7.3 Analysis Sets

Denovo opioid experienced subjects are defined as de novo subjects who are currently taking no less than 10 mg but no more than 60 mg MSE/day for at least the 7 days prior to signing the ICF

Denovo naive patients are defined as de novo subjects who are not opioid experienced subjects.

Safety Analysis Set: The Safety Analysis Set includes all subjects who received at least 1 dose of study drug. Analyses of safety will be summarized for this population.

Completers Analysis Set: All subjects in the Safety Analysis Set who complete 52-week exposure to NKTR-181.

Pharmacokinetic (PK) Analysis Set: The PK Analysis Set consists of all subjects who received at least 1 dose of NKTR-181 and have at least 1 PK data point available.

7.4 Definition of Visit Window

Deviations are to be expected between subjects in the actual number of study days from Day 1 to when planned visits are carried out. To handle this for tables, figures, listings, and analyses where data are to be grouped by visit, visit numbers will be defined according to [Table 1](#).

The following windows will apply only for summaries for value and change value by visit and summaries for abnormalities. If multiple assessments were performed within the visit window, the following will be applied:

- If there are multiple records in the same visit window, the measurement closest to the scheduled visit day will be used.
- If two visits are equidistant from the scheduled day, the later will be assigned to the visit.
- In the summaries for abnormalities, the worst case will be summarized for that visit regardless of how close to the scheduled visit it is.

Table 1: Windowed Visits for Summary

Visit	Scheduled Study Day	Windowed Visits for Labs	Windowed Visits for Vital Signs	Windowed Visits for ECG	Windowed Visits for CSSRS	Windowed Visits for mBPI	Windowed Visits for COWS
Baseline	First dose	<=first dose date	<=first dose date	<=first dose date	<=first dose date	<=first dose date	<=first dose date
The Titration visits		go with the actual visit	go with the actual visit	NA	NA	go with the actual visit	NA
Visit 10 - Stable Dose	1	Day 1	Day 1	Day 1	Day 1	Day 1	NA
Visit 11	30	Day2 to 45	NA	NA	NA	Day2 to 45	NA
Visit 12	60	Day46 to 75	NA	NA	NA	Day46to 75	NA
Visit 13	90	Day76 to 105	Day2 to 105	Day2 to 105	Day2 to 105	Day76 to 105	NA
Visit 14	120	NA	NA	NA	NA	Day106 to 135	NA
Visit 15	150	NA	NA	NA	NA	Day136 to 165	NA
Visit 16	180	NA	NA	NA	NA	Day165 to 195	NA
Visit 17	210	Day106 to 225	Day106 to 225	Day106 to 225	Day106 to 225	Day196 to 225	NA
Visit 18	240	NA	NA	NA	NA	Day226 to 255	NA
Visit 19	270	NA	NA	NA	NA	Day256 to 285	NA
Visit 20	300	Day226 to one day before visit 21	Day226 to one day before visit 21	Day226 to one day before visit 21	Day226 to one day before visit 21	Day286 to one day before visit 21	NA
Visit 21	357 from Titration Day 1	go with the actual visit	NA	NA	go with the actual visit	go with the actual visit	go with the actual visit
Visit 22	364 from Titration Day 1	go with the actual visit	go with the actual visit	go with the actual visit	go with the actual visit	go with the actual visit	go with the actual visit
3-day Safety Follow-up	3 days after ET visit	3 to 6 days after ET visit	3 to 6 days after ET visit	NA	NA	NA	3 to 6 days after ET visit
14-day Safety Follow-up	14 days after ET visit	>=7 days after ET visit	NA	NA	NA	NA	>=7 days after ET visit

Abbreviations: C-SSRS, Columbia-Suicide Severity Rating Scale; NA, not applicable.

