6.5 Monitoring of Hepatic Transaminases

Hepatic function testing (alanine aminotransferase [ALT], aspartate aminotransferase [AST], alkaline phosphatase [ALP], and total bilirubin [TBL]) will be performed according to the Schedule of Assessments (Section 1.2). In the event that an elevation of ALT or AST > 3 X ULN is observed in an individual study subject, the subject should be contacted immediately and the procedures in Table 1 should be followed. The Medical Monitor or

designee may be contacted for further discussion as needed. If a subject's study drug is interrupted for 3 days or more due to elevated hepatic transaminase levels, sponsor **must** be consulted prior to restarting study drug.

Table 1: Recommended Procedures for Subjects with Elevated Aminotransferase Test Results

Magnitude of Elevation in ALT or AST	Recommendation
> 3 to ≤ 8 X ULN	The subject should be seen for an unscheduled visit as soon as possible. At the unscheduled visit, the subject will be examined for clinical signs and/or symptoms of hepatic dysfunction [fatigue, nausea, vomiting, right upper quadrant pain or tenderness, fever, rash, and/or eosinophilia (> 5%)]. Repeat hepatic function tests should be performed. Review the subject's current list of concomitant medications to assess for confounding medications that could cause elevations in AST and/or ALT. The subject should return every 48 to 72 hours for examination and repeat hepatic function testing until all test values are ≤ 2.0 X ULN or return to baseline.
> 3 X ULN and hyperbilirubinemia (> 1.5 X ULN)	Study medication should be permanently discontinued.
> 3 X ULN with ongoing, unresolved symptoms such as fatigue, nausea, vomiting, right upper quadrant pain or tenderness, fever, rash or eosinophilia (> 5%)	Study medication should be permanently discontinued.
> 5 X ULN for ≥ 2 weeks	Study medication should be permanently discontinued.
> 8 X ULN	Study medication should be permanently discontinued.

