10.5 Twelve-Lead Electrocardiograms

Twelve-lead electrocardiograms (ECGs) will be performed on a calibrated 12-lead machine according to the Schedule of Assessments (Section 1.2). Subjects must be resting quietly in the supine position for at least 5 minutes before the 12-lead ECG. Interpretation of 12-lead ECGs and interval duration measurements will be performed by a designated ECG laboratory. Interpretation of ECGs and interval duration measurements will be provided to the site.

The Investigator or qualified sub-Investigator will review all ECG interpretations and interval duration measurements for clinical significance. During the treatment period, if an ECG is obtained and reveals that the subject's QTcF interval is > 500 msec or has an increase of ≥ 60 msec compared to baseline QTcF and confirmed with a second ECG within 30 minutes, treatment with study medication should be interrupted. In the event this occurs, the investigator should contact the Medical Monitor as soon as possible to discuss if the subject can continue on treatment or if the subject should stop study medication. Subjects who are discontinued will be required to complete the ET Visit and all safety follow-up procedures. Any ECG interpretation deemed to be clinically significant will be reported as an AE as described in Section 10.1.

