7.2 Study Day

- The day of the titration start (Visit 3 date) will be called Titration Day 1. Visit 10 is the end of titration, the dose at visit 10 is defined as stable dose. The day of the stable dose (Visit 10 date) will be called Day I. Study day will be calculated from the Day 1.
- Baseline is defined as the last non-missing observation prior to or on Titration Day 1. Change from baseline variables will be calculated as the post-baseline value minus baseline value.

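### SAP 7.4 gives the scheduled-visit record no priority, so an ALT/AST recheck prompted by a high result can replace an early scheduled value in the by-visit summaries at Visits 11, 12, 13, 17 and 20

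*SAP*

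**What the plan says.** SAP 7.4 sets the scope of the visit windows: "The following windows will apply only for summaries for value and change value by visit and summaries for abnormalities". When a window holds several records, the SAP says "If there are multiple records in the same visit window, the measurement closest to the scheduled visit day will be used" and adds "If two visits are equidistant from the scheduled day, the later will be assigned to the visit". Abnormality counts follow a different rule: "In the summaries for abnormalities, the worst case will be summarized for that visit regardless of how close to the scheduled visit it is". Neither rule mentions whether a record came from a scheduled or an unscheduled visit.

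Days are counted from Visit 10: "Study day will be calculated from the Day 1" (SAP 7.2). The laboratory targets are Days 30, 60, 90, 210 and 300 for Visits 11, 12, 13, 17 and 20. For titration visits and for Visits 21 and 22, Table 1 of the SAP says "go with the actual visit"; Visit 10 is Day 1 only.

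Three parts of the protocol bear on this:

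- **Visit timing (1.2).** Monthly visits are every 30 days with a tolerance of minus 3 and no plus. The anchor (previous visit or Day 1) is not stated.
- **Liver tests (6.5, Table 1).** For ALT or AST above 3 and up to 8 X ULN, an unscheduled visit takes place as soon as possible, and then "The subject should return every 48 to 72 hours for examination and repeat hepatic function testing until all test values are" at or below 2 X ULN or back at baseline.
- **Unscheduled visits (6.2).** They do not stand in for scheduled ones, so both records can exist.

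For QTcF, protocol 10.5 asks for a confirmatory ECG within 30 minutes, after which "treatment with study medication should be interrupted". SAP 8.7.6 presents vital-sign and ECG statistics for scheduled visits. SAP 8.7.5, on laboratory data, has no such limit.

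**The concern.** A selection rule for by-visit tables should not depend on the result being summarized. Here it can. A high ALT or AST generates a series of later tests in the same window, and an isolated normal result generates none under protocol 6.5. If the scheduled visit was early, a later test may lie nearer the target day, and the result that triggered the series drops out of the value and change tables. ALP and total bilirubin, drawn with ALT and AST, go with it.

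Long-term safety is the primary objective, and SAP 7.1 summarizes continuous data with SD and maximum as well as mean and median. A few high liver values show mainly in the maximum and SD. The value table and the abnormality table could then describe different blood draws for the same subject at the same visit, with nothing in the SAP to explain why.

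**Working it through.** The plan gives no figure on this point, so there is nothing to reproduce. The check applies the SAP 7.4 rule directly.

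**1. When a recheck wins.** Let T be the target day, V the day of the scheduled test and V + d the day of a later recheck (d > 0), both inside the window. With ties going to the later record, the recheck is used if |V + d − T| ≤ |V − T|. Squaring gives d² ≤ 2d(T − V), so d ≤ 2(T − V). A scheduled test on or after its target is never displaced by a later one.

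**2. Visit days.** Visits 11, 12, 13, 17 and 20 are k = 1, 2, 3, 7 and 10 intervals after Day 1. With intervals of 27 to 30 days from the previous visit, V runs from 1 + 27k to 1 + 30k: Days 28-31, 55-61, 82-91, 190-211 and 271-301. With exact 30-day intervals, V = 31, 61, 91, 211 and 301, always one day after target.

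**3. Chance that one recheck two days later wins.** The condition is V ≤ T − 1. With each interval uniform on {27, 28, 29, 30} (an assumption):

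- Visit 11: V = 28 or 29, 2/4 = 50%.
- Visit 12: V ≤ 59, 13/16 = 81%.
- Visit 13: V ≤ 89, 60/64 = 94%.
- Visit 17: only V = 210 (7 ways) and V = 211 (1 way) fail, 1 − 8/16,384, about 100%.
- Visit 20: only V = 300 (10 ways) and V = 301 (1 way) fail, 1 − 11/1,048,576, about 100%.

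**4. Other timings.** The documents give neither the distribution of visit timing nor the laboratory turnaround, so the range is:

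| Timing assumption | d = 2 | d = 3 | d = 5 | d = 7 |
|---|---|---|---|---|
| Every interval 30 days, all five visits | 0% | 0% | 0% | 0% |
| Uniform on T−3 to T, each visit | 75% | 50% | 25% | 0% |
| Uniform on T−3 to T+3, each visit (comparison only) | 43% | 29% | 14% | 0% |
| 27-30 days from previous visit: Visit 11 | 50% | 25% | 0% | 0% |
| Visit 12 | 81% | 63% | 38% | 19% |
| Visit 13 | 94% | 84% | 69% | 50% |
| Visit 17 | 100% | 99.8% | 99% | 98% |
| Visit 20 (recheck before Visit 21) | 100% | 100% | 100% | 99.9% |

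**5. Which record is used.** With rechecks at +3, +6 and +9 days and intervals of 27-30 days, the Visit 13 record is the scheduled one in 16%, the first recheck in 53%, the second in 30% and the third in 2%. At Visit 17 the third is used in 75%.

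**6. Size.** Suppose a share f of subjects is affected and all are displaced, with the recheck lower by D. The mean is then too low by f × D. For f = 0.5% to 2% (3 to 12 of 600) and D = 1 to 3 X ULN, that is 0.005 × 1 = 0.005 to 0.02 × 3 = 0.06 X ULN.

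For spread, an illustration with assumed inputs: ULN 40 U/L; 1% affected, with scheduled value 240 and recheck 80 U/L; all others mean 25, SD 12.

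- Mean: 0.99 × 25 + 0.01 × 240 = 27.15, against 0.99 × 25 + 0.01 × 80 = 25.55.
- SD: √(0.99 × 144 + 0.0099 × 215²) = 24.5, against √(0.99 × 144 + 0.0099 × 55²) = 13.1.
- Maximum among the affected subjects: 240, against 80 U/L.

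The assumed fall here is 4 X ULN, deliberately larger than the range used for the mean.

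**7. After the fix.** If the scheduled record is used whenever it lies in the window, displacement is 0% at all five visits under every timing above.

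**The case against.** The strongest objection is that the peak is not lost. The worst-case rule protects abnormality summaries, and out-of-range results are flagged in listings. That stands, and it confines the point to value and change tables. It is also true that displacement needs early visits, that the documents do not say visits will drift, and that the median would barely move.

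A reader might infer that the rule systematically takes liver, QTcF and vital-sign values after recovery or off drug. The documents do not support this:

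- **Systematic.** Frequency runs from 0% to about 100% on timing the protocol leaves open.
- **After recovery or off drug.** For an isolated rise of more than 3 and up to 8 X ULN, protocol Table 1 directs repeat testing, and at Visit 13 the record used is most often the first recheck. With strong drift at Visits 17 and 20, a later recheck may be used and might show recovery; that is possible, not established.
- **One direction.** Unscheduled visits also occur for intolerance, so a normal scheduled value could be replaced by one from a symptomatic subject.
- **QTcF.** The mandated repeat is on the same day and precedes interruption.
- **Vital signs.** No recheck after an abnormal reading is mandated.

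For ECG and vital signs, SAP 8.7.6 appears to shut out unscheduled records, although it is not reconciled with 7.4. None of this answers the liver-test case, where rechecks are mandated, their trigger is the result itself, and SAP 8.7.5 has no scheduled-visit limit.

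**Conclusion.** The point holds for ALT and AST, and for ALP and total bilirubin drawn with them, in by-visit value and change summaries at Visits 11, 12, 13, 17 and 20. The rule lets the result of a scheduled test influence whether that test is tabulated. How often cannot be settled from the documents: it never happens with exact 30-day intervals and is frequent from Visit 12 onward if intervals shorten within the permitted 3 days and accumulate.

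The likely effect on the mean is small. The maximum and SD can change more, by an amount that rests entirely on the assumed share of subjects and size of fall. Abnormality summaries, titration visits and Visits 10, 21 and 22 are not exposed to a later-day substitute. For QTcF and vital signs, what remains is an unreconciled wording between SAP 7.4 and 8.7.6, relevant only if non-mandated unscheduled records compete. This is a low-cost correction worth making, not a threat to the safety conclusions as a whole.

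**What to change.** Replace the closest-record sentence in SAP 7.4 with:

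> For value and change summaries the scheduled-visit record is used when present in the window (if more than one, the closest to the nominal day); an unscheduled or repeat record is used only if no scheduled-visit record lies in the window, and then the closest one.

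The parenthesis is needed because two scheduled records can share a window. With every interval at 27 days, Visit 16 falls on Day 1 + 6 × 27 = 163, inside the Visit 15 mBPI window (Days 136-165).

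Keep the worst-case rule for abnormality summaries, and align SAP 8.7.6 with the new sentence so that laboratory, ECG and vital-sign tables follow one convention.

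The cost is one sentence and a sort order in the programs, with no extra data. Tabulated maxima may look slightly less favourable.

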1.1 Study Schematic

1.2 Schedule of Assessments

Assessment Period	Screening Up to 21 days		Treatment* 52 weeks							Follow-Up 14 days		Unscheduled Visit
	1	2 ¹	3	4, 5, 6, 7, 8, 9 (Flexible)	10, 13, 17, & 20	11 & 12	14-16 & 18-19	21/ET ²	22/EOT	23	24/EOS	
Dayse	≤ 21 days prior to Visit 3		1	Every 4-10 Days after previous visit	Every 30 (- 3)	Every 30 (- 3)	Every 30 (- 3)	D357 (+ 3)	D364 (+ 3)	72 hours	14 (± 2)	
Written informed consent	X											
Inclusion/exclusion criteria	X	X	X									
Demographics ³	X											
PHQ-8 ⁴	X											
Medical history ⁵	X											
Alcohol breath test ⁶	X											
Physical examination ⁷	X											
Vital signs ⁸	X		X	X	X				X	X		X
12-lead electrocardiogram ⁹	X				X				X			X
Clinical laboratory tests ¹⁰	X		X	X	X	X		X	X	X	X	X
Pregnancy test ¹¹	X		X		X				X			X
Urine drug screen ¹²	X		X	X	X							
eC-SSRS ¹³	X		X		X			X	X			
Taper opioid analgesics ¹⁴		X										
Dose titration assessment				X								
mBPI-SF ¹⁵			X	X	X	X	X		X			X
COWS		X ¹⁶	X ¹⁶					X	X	X	X	X
SOWS ¹⁷		X						X	X	X	X	
PK blood sample collection			X ¹⁸	X ¹⁹	X	X		X	X			X
Discontinue current analgesics			X									
Dispense/review/collect/instruct study drug			X	X	X	X	X	X ²⁰	X ²¹			X
Opioid side effect training			X									
Abuse & diversion assessment				X	X	X	X		X			X
Concomitant medications ²²			←									X
Adverse events ²²			←									X

Abbreviations: ALP, alkaline phosphatase; ALT, alanine aminotransferase; AST, aspartate aminotransferase; BMI, body mass index, COWS, Clinical Opiate Withdrawal Scale; eC-SSRS, electronic Columbia–Suicide Severity Rating Scale; ECG, electrocardiogram, EOS, end of study; EOT, end of treatment; ET, early termination; mBPI-SF, modified Brief Pain Index-Short Form; MSE, morphine sulfate equivalent; NRS numerical rating scale; PHQ-8, Personal Health Questionnaire Depression Scale PK, pharmacokinetic; SOWS, Subjective Opiate Withdrawal Scale; TBL, total bilirubin.

* If at any time a subject does not tolerate study drug between protocol-mandated visits in the Treatment Period, per Investigator discretion, an unscheduled visit should occur.

FOOTNOTES:

1. There is no Visit 2 for Rollover Subjects.
2. If a subject was dosed with study drug and discontinues from the study before completing all of the scheduled assessments, then assessments for Visit 21/ET and all safety follow-up procedures should be completed for this subject.

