8.6.1 Responder Rates Based on mBPI Pain Intensity

Pain intensity score reduction based on the mBPI Pain Intensity subscale for each visit will be used to classify responder where:

Pain intensity score reduction = (mBPI Pain Intensity change from visit 3/visit 3 mBPI Pain Intensity)*100.

Three responder rates will be calculated at each time point, where responders are defined as subjects with:

- Pain intensity score reduced by 30% from visit 3 mBPI Pain Intensity,
- Pain intensity score reduced by 50% from visit 3 mBPI Pain Intensity,

- Pain intensity score reduced according to multiple cut-offs of 10% increments from the visit 3 mBPI Pain Intensity.

Responder rate = (no. of responders / total no. of subjects)*100, where total no. of subjects is the number of all the subjects in the analysis set. Subjects, who discontinue prior to the time point or have a missing pain score at that time point, will be counted as non-responders.

The number and percentage of responders in each dose level for pain intensity score reduction according to multiple cut-offs of 10% increments from baseline will be presented.

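### Fixed 30-day mBPI windows do not follow monthly visits that may come early but never late, so the late pain scores of compliant subjects can be dropped or reported one visit too soon

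*SAP*

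**What the plan says.** Protocol 1.2 (Schedule of Assessments) spaces Visits 10 to 20 at 30 days with a tolerance of minus 3 and no plus, so 27 to 30 days. The cell does not say what the 30 days are counted from. The neighbouring titration cell does: "Every 4-10 Days after previous visit".

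SAP 7.2 makes the Visit 10 date Day 1 and states: "Study day will be calculated from the Day 1". SAP 7.4, Table 1, schedules Visits 11 to 20 at Days 30, 60, ... 300. Its mBPI windows include Visit 17 at Days 196–225, Visit 18 at Days 226–255, Visit 19 at Days 256–285, and Visit 20 at "Day286 to one day before visit 21". Where records compete: "If there are multiple records in the same visit window, the measurement closest to the scheduled visit day will be used". For titration visits and Visits 21 and 22, the same table keeps the visit as it actually occurred.

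SAP 7.4 gives the windows two scopes. For "tables, figures, listings, and analyses where data are to be grouped by visit, visit numbers will be defined according to" Table 1. Then: "The following windows will apply only for summaries for value and change value by visit and summaries for abnormalities".

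SAP 8.6.1 says: "Pain intensity score reduction based on the mBPI Pain Intensity subscale for each visit will be used to classify responder". Subjects who discontinued before the time point or "have a missing pain score at that time point, will be counted as non-responders", with the whole analysis set as denominator.

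**The concern.** A tolerance that runs only one way can build up over ten intervals, while the windows stay fixed. Drift of up to 3 days per interval can exceed the roughly 15-day half-width of a window, and a visit made entirely within the protocol then falls into the window of the visit before it. The mBPI-SF is the only efficacy endpoint and carries the secondary objective. At stake are real on-treatment scores at the late visits, which may be discarded, moved back a month, or lost from the Visit 20 row. The Schedule has no mBPI-SF at Visit 21, and Visit 22 follows the taper, so on that schedule Visit 20 is the last planned pain score before the taper.

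**Working it through.** **Reproducing the plan's windows.** Scheduled day = 30 × (v − 10); window = scheduled day − 14 to + 15. This gives every printed mBPI bound for Visits 12 to 19 and the Visit 20 lower bound (300 − 14 = 286), with one exception. Visit 16 should start at 180 − 14 = 166 but is printed as 165. Visit 15 ends at 150 + 15 = 165, so Day 165 belongs to both windows. (Visit 11 starts at Day 2 by design.)

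**Placing compliant visits.** With Visit 10 on Day 1 and constant spacing d counted from the previous visit, Visit v falls on Day 1 + d × (v − 10).

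| Visit | mBPI window | d = 27 | d = 28 | d = 29 | d = 30 |
|---|---|---|---|---|---|
| 15 | 136–165 | 136 | 141 | 146 | 151 |
| 16 | 165–195 | 163 | 169 | 175 | 181 |
| 17 | 196–225 | 190 | 197 | 204 | 211 |
| 18 | 226–255 | 217 | 225 | 233 | 241 |
| 19 | 256–285 | 244 | 253 | 262 | 271 |
| 20 | from 286 | 271 | 281 | 291 | 301 |

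- *28 days.* Days 197 and 225 share the Visit 17 window. They are 13 and 15 days from Day 210, so the closest-record rule keeps the true Visit 17 and drops the true Visit 18. Day 253 is reported as Visit 18 and Day 281 as Visit 19. No scheduled record enters the Visit 20 window.
- *27 days.* Days 136 and 163 share the Visit 15 window, 14 and 13 days from Day 150, so the true Visit 16 displaces the true Visit 15. Visits 17 to 20 each move down one label, and the Visit 20 window has no scheduled record.
- *29 or 30 days.* All visits are labelled correctly.

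**Threshold.** Visit v falls below its window's lower bound L when the mean spacing is less than (L − 1)/(v − 10):

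- Visit 18: 225/8 = 28.13 days
- Visit 19: 255/9 = 28.33 days
- Visit 20: 285/10 = 28.5 days

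**How often.** The documents give no distribution of intervals, so these are assumptions, with gaps independent.

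| Assumed spacing | Visit 20 before Day 286 |
|---|---|
| Uniform on 27, 28, 29, 30 days | 44% (Visit 19 mis-windowed 28%, Visit 18 14%) |
| Uniform on 28, 29, 30 days | 1.5% |
| 29 or 30 days | 0% |
| Each visit 0 to 3 days before Day 30, 60, ... 300 | 0% |

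**Other columns of Table 1.** At 28-day spacing Visits 13, 17 and 20 fall on Days 85, 197 and 281. These lie inside the laboratory, vital-sign, ECG and C-SSRS windows, so the problem is confined to mBPI.

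**Responder rates, if Table 1 governs them.** With 44.5% of subjects lacking a windowed Visit 20 score, drift unrelated to response and no unscheduled record filling the gap, a true 60% rate would be reported as 60% × (1 − 0.445) ≈ 33%. If responder rates use the actual visit, the loss from this source is zero.

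**The case against.** **Scope.** The strongest objection concerns the responder rates. A reader might infer that compliant subjects will be scored as Visit 20 non-responders and that a 60% rate will be reported as 33%. The documents do not establish this. The sentence limiting the windows to value, change and abnormality summaries does not name responder rates; the sentence before it covers all analyses grouped by visit. The two conflict, and the plan does not say which prevails. This objection stands: the non-responder consequence is conditional.

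**Anchor.** Cumulative drift is an inference. If visits were meant to be tied to Days 30, 60, ... 300, matching Table 1, nothing is mis-windowed. This also stands as a limit, although neither document states such an anchor, and an interval repeated every 30 days is most naturally counted from the visit before.

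**Frequency.** The 44% needs spacing uniform over the full permitted range, which nothing in the documents supports. Visit 21 is also fixed at Day 357 from titration Day 1. If Visit 10 falls on titration Day 36 (an assumption based on the 5-week titration), 28-day spacing leaves 357 − 36 − 280 = 41 days between Visits 20 and 21. That sits awkwardly with a monthly schedule, but it is not prohibited. An unscheduled mBPI-SF in that gap could fill the Visit 20 window, though the true Visit 20 would still be reported as Visit 19.

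**Labels by elapsed time.** Windowing by time is a legitimate choice: Day 281 is 11 days from Day 270 and 19 from Day 300. That defends the Visit 19 label. It does not defend discarding a compliant Visit 18 score or leaving the Visit 20 row without a scheduled record.

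**Last pre-taper score.** The Schedule has no mBPI-SF at Visit 21, but protocol 6.2 and SAP 8.6 call for it at each visit and Table 1 has a Visit 21 entry. Calling Visit 20 the last score before the taper therefore rests on the Schedule alone.

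**Conclusion.** The point holds for the by-visit mBPI value and change summaries, to which the windows apply under either scope sentence. Provided each interval runs from the previous visit, a compliant subject on a 28-day rhythm loses the Visit 18 score, has Visits 19 and 20 reported one visit too soon, and has no scheduled Visit 20 record. The share of subjects affected at Visit 20 runs from 0% to about 44% across the assumed spacings and cannot be fixed from the documents.

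The effect on responder rates is a possibility created by the conflicting scope sentences, so the 33% figure is an illustration of one reading and not an expected result. The Day 165 overlap is a separate one-day error that does not depend on drift.

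The reach is limited. This is an uncontrolled, open-label safety study, the mBPI-SF is secondary and mainly descriptive, and at 28-day spacing the safety windows are unaffected. The change is still worth making, because it keeps collected scores in the summaries of the only efficacy endpoint.

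**What to change.** In SAP 7.4, Table 1, mBPI column:

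1. Assign scheduled Visits 10 to 20 by the visit as it actually occurred, the rule the table already uses for titration visits and Visits 21 and 22. Use day windows only to place unscheduled records.
2. Reconcile the two scope sentences, and state that the responder rates in SAP 8.6.1 use the same visit assignment as the value and change summaries.
3. Start the Visit 16 window at Day 166.

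The cost is SAP wording and one programming rule, with no new data. The downside is that nominal visit labels track elapsed time less closely when visits drift.
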